## Data Safety and Monitoring Board

This project is funded as a Pilot Study through the UF Claude D. Pepper Older Americans Independence Center (OAIC) grant (NIH P30 AG028740 ) and thus uses the OAIC Data Safety Monitoring Board (DSMB).

The OAIC DSMB consists of an established board which has reviewed all studies conducted within the UF OAIC during for the past seven years. This board meets annually. DSMB Reports will be provided to the UF IRB-01 with annual Continuing Review submissions.

## Confidentiality

Confidentiality of data is maintained by using research identification numbers or alphanumerics that uniquely identify each individual. Phone pre-screener will be de-identified by replacing identifiable information with numbers or alphanumerics. Collected data will be used only for research purposes, and publications will not contain any individual identifiers. Safeguards are established to ensure the security and privacy of participants' study records. The research records are kept in a locked room in locked computer files and file cabinets. Storage Areas for all records containing PHI or other restricted information is physically secure and environmentally controlled, to protect the records from unauthorized access and damage or loss from temperature fluctuations, fire, water damage, pests, and other hazards. Only study personnel have access to these files. After the study is completed, local data are stored with other completed research studies in a secured storage vault. According to the HIPAA rules, consent forms signed by the study participants, the study's research records containing identifiable data will be stored for a minimum of 6 (six) years after the study is completed and closed with IRB.

In compliance with the Health Insurance Portability and Accountability Act (HIPAA) and the Standards for Privacy of Individually Identifiable Health Information of the Department of Health and Human Services, study staff accesses personal health information and medical records only after receiving informed consent (verbal for phone screener and signed for short form and main consent).

## 4. POSSIBLE DISCOMFORTS AND RISKS

---

**400-m walk:** The 400-meter test may be associated with the risk of falling or development of chest discomfort due to coronary ischemia or dyspnea due to heart failure or lung disease. Rarely, falling during the 400-meter walk test may result in a fracture. Similar to the six-minute walk test, completion of the SPPB may be associated with the risk of falling or development of chest discomfort due to coronary ischemia or dyspnea due to heart failure or lung disease. Rarely, falling during the SPPB test may result in a fracture. In our experience conducting thousands of 400 m walk tests on individuals within various studies, the risk of falling is less than 1/500 and the risk of a fracture-associated fall is less than 1/5000. In the LIFE study we have performed approximately 10,000 400 m walk tests with no safety concerns raised by the DSMB.

**Questionnaires:** There are some risks associated with questionnaire administration. Sensitive information collected for this study includes lifestyle factors (e.g., alcohol use) and personal health information (PHI) and are used predominantly in screening for eligibility and safety. Participation includes a risk of loss of confidentiality of this information.

To minimize risk, questionnaire data are collected in secure spaces where the interview cannot be overheard. Participants are reminded that they can decline to answer questions that are uncomfortable or concerning. All research staff members complete annual HIPPA for Researchers training as required by UF.

**DXA:** DXA scans to determine body composition involve small amounts of radiation exposure. The amount of radiation exposure from each whole body DXA scan is <2.5 mRem per scan. Although the potential long-term risk from these radiation doses is uncertain, such doses are exceedingly low and have never been associated with any definite adverse effects.

**Resistance Training:** Potential risks associated with RT will be explained to each participant by appropriately trained clinical site staff during the initial informed consent, screening, and study orientation.

- Difficulty breathing and/or shortness of breath
- Muscle, joint strains and soreness
- Soft tissue injury, falls and fractures
- Increasing intraocular and systemic pressures associated with use of the Valsalva maneuver to levels that may cause injury (detached retina, hernia, conjunctival hemorrhage), which is greatly reduced by instruction in proper exercise technique.
- Hernia
- Exacerbation of arthritis or other joint conditions
- Lumbar disk hernia
- A small increase in the risk of sudden death, stroke, and acute MI occurring during a bout of vigorous exercise has been reported, especially in previously sedentary individuals.
- Orthostatic hypotension
- Triggering of an asthma episode

These risks are minimized in all exercise sessions by having supervised and trained exercise interventionists who instruct participants in the proper exercise techniques, including instructions to breathe normally during the exercise. Procedures to minimize injury include warm-up and cool-down activities that include large muscle movements and stretching. The preparatory phase is designed so that participants can learn proper exercise technique and gradually increase training volume and intensity.

The entire exercise intervention is conducted on-site and all sessions are supervised by trained interventionists, who will monitor potential adverse experiences and symptoms. During the exercise sessions, a defibrillator and on-site trained staff are available to deal with medical emergencies.

To minimize these risks, research staff are trained in the conduct of all physical performance tests and certified by before they work with study participants. Study staff are instructed not to perform these tests if they feel that testing is unsafe for an individual participant or if the participant is concerned about safety. If safety concerns are identified by either the study staff or the participant during the testing procedures, testing is halted and the participant is not allowed to complete the test. In either case, the participant is assessed to determine the need for medical intervention and the cause for concern is evaluated. All study staff are trained in activating the emergency response system at The University of Florida's Institute on Aging facility.

All sessions are conducted by research staff trained to monitor potential adverse experiences and symptoms during the testing sessions. All personnel associated with the study have completed Basic Life Support (BLS) training and education on management of acute events including syncope, chest pain, acute dyspnea, focal neurological symptoms and abnormal vital signs. Additionally, a study physician is available on call and contact numbers for emergency services are posted. Institutional and community EMS services will be activated if needed.

Participants will be instructed to talk with the investigators about any discomforts that occur during the study. If a participant reports an injury, chest pain, leg swelling, excessive shortness of breath, palpitations, or dizziness, he/she will be referred to medical attention (his/her doctor, or Emergency Department).

All research staff complete human participants training required by The University of Florida institutional review board (IRB) and National Institutes of Health (NIH).

## **Adverse events (AE) and serious adverse events (SAE)**

The study will collects and reports only Serious Adverse Events (SAEs) and (nonserious) AEs associated with the intervention or study procedures. Pre-existing conditions and preplanned procedures (surgeries or therapies) scheduled prior to signing the Informed Consent are not considered AEs/SAEs.

**Adverse events (AE):** For this study's purposes, an AE or experience is defined as any health-related unfavorable or unintended medical occurrence that happens after randomization. Examples of AEs include, but are not limited to, the following:

- A clinically significant laboratory or clinical test result at follow up assessments
- An event that requires a visit to a physician because it alters the participant's ability to exercise
- An event that occurs as a result of a study procedure which is not listed in the Risks section of the consent

**Serious adverse events (SAE):** SAEs are defined as events that may be harmful to the participant and/or may be serious enough to warrant either temporary or permanent discontinuation of the study intervention or study procedures,

either because they are intolerable or because they are judged to be potentially harmful. Consistent with NIH guidelines, SAEs are AEs that meet any of the following criteria:

- results in death
- is life-threatening
- requires inpatient hospitalization
- prolongs an existing hospitalization
- results in a persistent or significant disability/incapacity
- important medical events that investigators judge to represent significant hazards or harm to
  - participants, and may require medical or surgical intervention to prevent one of the other SAEs
  - listed in this definition (e.g., hospitalization, death, persistent disability)

**Relationship to study intervention:** The classification of potential relationship to the intervention is as follows.

- Not Related – AE is clearly not related to the intervention or procedure (e.g., temporal sequence of events is not consistent with administration of intervention or procedures, other causes are more plausible or causal relationship is implausible).
- Possibly Related – AE that follows reasonable sequence from administration of intervention or procedure but that could readily have been produced by several other factors.
- Definitely Related – AE is clearly related to the intervention or procedure (e.g., follows reasonable temporal sequence from administration of the study intervention or procedure, confirmed by improvement after stopping intervention or procedure, and reappearance on repeated exposure to intervention or procedure, and cannot be explained by participants clinical or health status).

**Expected AE's:** Expected AEs are defined as anticipated events based on the prior experience with the intervention and listed in the participant consent and protocol; these can be attributed to an underlying condition or the patient population being studied. These conditions that may be unpleasant and bothersome to the participant, such as sore muscles, muscle or joint pain, or breathing problems, do not require discontinuing the study intervention or components of the intervention.

**Unexpected Adverse Events:** Unexpected adverse events (UAEs) are defined as events that occur during participation in the study but do not commonly occur in the study population and are

not listed in the informed consent. An AE is not defined as a UAE unless it meets all three defining criteria:

- unexpected given the research procedures described in the informed consent and characteristics of the study population;
- definitely related or possibly related to participation in the study intervention or procedures;
- suggests that the research intervention or procedures place participants or others at greater risk of harm than was previously realized.

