### 3. SPECIFIC AIMS / OBJECTIVES

#### Primary objective

- To evaluate the feasibility of implementing the D3Cr method in a resistance training trial as it relates to participant adherence, retention, training program design aspects (intensity, volume, frequency & safety) sample size, and cost of the main study.

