## Interventions

**Resistance Training Intervention:** The 14-week supervised resistance training intervention will include a full body, resistance training performed three days per week. The intensity, volume, tempo, and progression will be based on the Federal Physical Activity guidelines as shown in Table 2.

Exercises: The resistance training exercises will include mainly multi-joint exercises using selectorized machines to minimize training duration and maximize the benefit. Each session will include upper body exercises (Chest Press, Shoulder Press, Seated Rows) and lower body exercises (Leg Press, Leg Extension and Leg Curls, and Calf raise) that will be tailored to the participant needs. Interventionists will supervise all exercise sessions.

Warm up & cool down: Each training session will begin with 1 set of warm-up at a lighter load for 8–10 repetitions on 1 multi-joint upper body and 1 lower body machine. Each session will end with a 5 min cool-down involving stretching exercises and light calisthenics

Preparatory phase: Considering the participants are low functioning; we will use a 2-week *preparatory phase*, which will ensure sufficient time for connective tissue adaptations and for the participants to learn proper lifting form and breathing technique.

Training Phase: The training phase will last for 12 weeks and will be divided into 2 phases as shown in Table 2.

Intensity: The intensity will be maintained at 6-8 (moderate to vigorous RPE) as recommended by ACSM for older adults and the sets will be done until volitional fatigue. The CR-10 BORG's scale ranges from 1-10 will be used to document perceived exertion during resistance training.

Progression: The load will increase when participants can perform all repetitions in all sets .

Table 2. Resistance training parameters		
Preparatory Phase		Training Phase
	Week 1-2	Week 3-5
Days/wk	3	3
Sets * Reps	1-2* 12-15	3 *12-15
RPE	6 - 8	6 - 8
Rest (min)	1	1
Progression		Can do 3 sets of 15
		Can do 3 sets of 10

Note: All values are subject to change based on participant availability and ability of the participant to conduct the number of sets and reps prescribed.

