**Successful Aging:** The comparator group will meet every 2 weeks. Weekly workshops will include flexibility exercises and presentation topics related to older adults, such as preventive services and screenings, finding credible health information, and so forth. We instruct all control participants not to change their PA levels and the importance of remaining weight stable throughout the study period. The rationale for the health education group in place of a sedentary control is to minimize the social interaction effects and to minimize participant drop-outs.

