### **Adherence**

Adherence involves both attendance to scheduled sessions as well as the quality of the training that occurs during each session. Adherence to the exercise protocols are affected by personal, social and environmental factors. At a personal level, it is important to ensure that the goals of each participant are realistic. We recognize that social interactions between staff and participant as well as the broader social environment surrounding the study influence adherence. All staff will be instructed to engage with and be supportive toward all participants. We will also adopt a number of other strategies to improve attendance and quality of training sessions. Some strategies include, having trained interventionists to supervise training, including a preparatory phase to educate the participants about proper lifting technique, tailoring the training program based on the physical needs of the participant, maintaining a workout log to help motivation, monitoring missed visits so that the study coordinator can take prompt action and so forth

The physical environment and accessibility influence adherence. This includes such factors as ease of parking, transportation, and accommodations made for friends or significant others who may come to

training facilities to support participants via transportation, etc. At the time of baseline assessments, staff discuss these topics with each participant to be certain there are no significant barriers in this domain and/or to problem solve potential challenges that exist.

The comparator group will not participate in a resistance training intervention and hence pose a greater risk of dropping out. We expect, based on our previous experiences, that the flexibility exercises and health education classes offered every 2 weeks will serve an effective “active control” that will help to promote retention in the study. We will also provide an exercise prescription and education materials at the end of the study duration so that they can start a resistance training program outside the site.

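### Non-serious adverse events are kept only if linked to the intervention or procedures, and training sessions are monitored more closely than education sessions, so non-serious event counts cannot be compared between arms

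*Combined protocol and SAP*

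**What the plan says.** The section on adverse events defines an adverse event broadly, as "any health-related unfavorable or unintended medical occurrence that happens after randomization". The study nevertheless collects "only Serious Adverse Events (SAEs) and (nonserious) AEs associated with the intervention or study procedures". On the natural reading, serious events are collected whatever their cause, and non-serious events only if linked to the intervention or a procedure.

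The same section grades relatedness as not, possibly or definitely related. The middle grade is an "AE that follows reasonable sequence from administration of intervention or procedure but that could readily have been produced by several other factors". The protocol does not say who makes this judgement or whether that person knows the arm. Trial Design calls the study single-blind without saying who is blinded.

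Contact differs by arm. Under Interventions, RT is a "14-week supervised resistance training intervention", with "resistance training performed three days per week". For HE the text says "The comparator group will meet every 2 weeks", and its next sentence describes the workshops as weekly. The Adherence section refers to "health education classes offered every 2 weeks".

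The risks section says that the staff supervising exercise sessions watch for adverse symptoms. It makes no such statement for HE workshops. It says the same of testing sessions, which both arms attend, and all participants are told to raise any discomfort with the investigators. No scheduled questioning about adverse events, the same in both arms, is described.

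The primary objective covers "training program design aspects (intensity, volume, frequency & safety"). The Statistical plan contains no adverse event analysis.

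**The concern.** Relatedness decides which non-serious events are recorded at all, when it should be judged after recording. The judgement also depends on arm. It rests partly on timing relative to the intervention, and with three training days a week most events in RT follow a session closely. The same event in HE may fall many days after a meeting. Events in RT also have more chances to be noticed, because staff are watching at every session.

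The events most affected are those common at age 70 and over, such as joint pain, muscle soreness and falls without serious consequences. The protocol itself says that expected events can be due to an underlying condition or to the population studied. For these, HE is the only source in the trial for a background rate. If HE events are filtered out or never heard of, a count in RT cannot be separated into what training caused and what would have happened anyway. That weakens what the pilot can say about training safety when the main trial is designed.

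**Working it through.** The documents state no contact ratio, adverse event rate or recall period, so there is no figure of the plan's own to reproduce on this point. The only related figure is the sample size: 12 per group with 20% loss gives 12 × 0.80 = 9.6, stated as 10 evaluable.

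**1. Scheduled contact, from Interventions and Adherence**

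- RT: 3 sessions per week × 14 weeks = 42.
- HE every 2 weeks: 14 / 2 = 7, ratio 42 / 7 = 6.0.
- HE weekly: 14, ratio 42 / 14 = 3.0.

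Assessment visits are common to both arms and dilute the ratio. Their number is assumed here to be 2 to 6:

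- HE every 2 weeks: (42 + 2) / (7 + 2) = 4.9, down to (42 + 6) / (7 + 6) = 3.7.
- HE weekly: (42 + 2) / (14 + 2) = 2.8, down to (42 + 6) / (14 + 6) = 2.4.

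RT contact is higher on every reading.

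**2. What unequal contact could do (illustration, all inputs assumed)**

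Suppose that an event is noted only if a session falls within w days of it. The share captured is min(1, 3w/7) in RT, and min(1, w/14) or min(1, w/7) in HE.

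| w (days) | RT | HE, 2-weekly | Ratio | HE, weekly | Ratio |
|---|---|---|---|---|---|
| 2 | 0.86 | 0.14 | 6.0 | 0.29 | 3.0 |
| 3 | 1.00 | 0.21 | 4.7 | 0.43 | 2.3 |
| 5 | 1.00 | 0.36 | 2.8 | 0.71 | 1.4 |
| 7 | 1.00 | 0.50 | 2.0 | 1.00 | 1.0 |
| 14 | 1.00 | 1.00 | 1.0 | 1.00 | 1.0 |

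In this model the ratio of sessions is the upper bound on the ratio of events captured, and the range includes no distortion.

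**3. What the relatedness filter could do (illustration, all inputs assumed)**

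Take the same true risk in each arm, 6 of 12 participants. The false risk difference is 0.5 × (share kept in RT − share kept in HE).

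- Keep 50% and 50%: 3.0 against 3.0 events, difference 0.
- Keep 50% and 25%: 3.0 against 1.5, difference 12.5 points.
- Keep 60% and 10%: 3.6 against 0.6, difference 25 points.

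The documents give no basis for choosing among these. They support a likely direction, not a size.

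**4. How often a common checklist would have to be given**

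Under the model in step 2, a checklist given only at week 8 and post-test leaves a gap of about 56 days before week 8. For w of 3, 7 and 14 days it would capture 3/56 = 5%, 7/56 = 12.5% and 14/56 = 25%. That is equal in both arms but poor. Every 2 weeks, it captures 3/14 = 21%, 7/14 = 50% and 14/14 = 100%, again equal in both arms.

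**The case against.** The strongest reply is that nothing in the plan is damaged. Safety enters the primary objective as a feature of the training program, the secondary objectives do not mention it, and the Statistical plan compares no adverse events between arms. Related events in RT plus all serious events largely serve that purpose. The protocol's stated reasons for using HE are to limit social interaction effects and drop-out, not to supply a background event rate. Even an unbiased comparison would be imprecise. With 12 per arm and an assumed 50% risk, the 95% interval for a risk difference is about ±1.96 × √(2 × 0.25 / 12) = ±40 points.

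Most of this stands, and it makes the point one about descriptive counts. It does not remove it. With no planned analysis, any statement about training safety will rest on the recorded counts, and events never recorded cannot be added later.

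It is also fair to say that a broad definition with a narrower collection rule is a choice of scope, not a contradiction. The unrelated grade is still needed for serious events.

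A reader might infer that a planned safety comparison is biased by design, that RT is seen six times as often as HE, and that the HE count will fall to nearly zero. The documents do not support this:

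- No such comparison is planned.
- Six is the ratio for intervention sessions only, on the two-weekly reading.
- HE events can qualify. HE includes flexibility exercises and study tests, possibly related events are kept, and both arms may report discomfort at any time.
- The documents do not say that someone who knows the arm judges relatedness.

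**Conclusion.** The point holds for non-serious events. The collection rule, together with monitoring at intervention sessions that is described only for RT and scheduled RT contact 3 to 6 times that of HE, makes non-serious counts non-comparable between arms. The contact range falls to about 2.4 to 4.9 if 2 to 6 common assessment visits are assumed. A skew toward RT is probable. Its size cannot be derived, because the recall periods and shares kept used above are assumptions and some of them give no skew.

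Serious events escape the filter, although unequal contact could affect how soon they are learned of. This is a weakness in descriptive safety data from a 24-person pilot, not a fault in a prespecified analysis. It merits a change because training safety is in the primary objective and the remedy is cheap.

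**What to change.** - Amend the adverse event section so that all adverse events are recorded in both arms regardless of relatedness.
- Use one short structured checklist (falls, pain, injury, medical visits) at the same interval in both arms, each time covering the period since the last one. Every 2 weeks at existing sessions, plus the week 8 and post-test visits, would work on either reading of the HE frequency.
- Classify relatedness afterwards, by someone unaware of arm where feasible, and name that role in the protocol.
- Add to the Statistical plan that checklist events are reported descriptively by arm, and that events noted only at RT sessions are listed separately.
- Reconcile the two statements of HE meeting frequency.

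The cost is at most 7 two-weekly forms plus 2 visit forms per participant, or 9 × 24 = 216 short forms, and a modest number of extra unrelated events to record. No additional visits are needed.

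### The plan defines a serious adverse event in two inconsistent ways, so a temporary stop of training for pain is serious under one sentence and nonserious under the next

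*Combined protocol and SAP*

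**What the plan says.** All of the relevant rules stand under Adverse events (AE) and serious adverse events (SAE).

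- **Opening definition.** "SAEs are defined as events that may be harmful to the participant and/or may be serious enough to warrant either temporary or permanent discontinuation". What stops may be the intervention or a study procedure, and the stated grounds are that such events warrant it "either because they are intolerable or because they are judged to be potentially harmful".
- **Criteria list.** The next sentence, which refers to NIH guidelines, says that "SAEs are AEs that meet any of the following criteria". The six criteria are death, threat to life, inpatient admission, a prolonged hospital stay, lasting or significant disability, and an important medical event as judged by the investigator. Discontinuation is not among them.
- **Collection rule.** "The study will collects and reports only Serious Adverse Events (SAEs) and (nonserious) AEs associated with the intervention or study procedures".
- **Relationship.** The classes are Not Related, Possibly Related and Definitely Related. Possibly Related covers an event that follows plausibly in time but could have had other causes.
- **Expected AEs.** These are symptoms "such as sore muscles, muscle or joint pain, or breathing problems, do not require discontinuing the study intervention or components of the intervention", and "these can be attributed to an underlying condition or the patient population being studied".

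The Primary objective includes "training program design aspects (intensity, volume, frequency & safety) sample size, and cost of the main study".

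**The concern.** In a trial of high-intensity training in people aged 70 or over with an SPPB score of 8 or less, resting someone for a week because of shoulder or knee pain is foreseeable. The two definitions class that event differently, and no sentence ranks them. The paragraph on expected AEs does not help: it describes pain that does not require stopping and leaves pain that does stop training without a class.

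Safety of the programme is one of the things the pilot is meant to establish for the main trial. With 12 participants per arm, relabelling one or two people visibly changes the SAE table. Two coordinators following the same text in good faith could produce different tables from the same events.

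**Working it through.** The plan states no figure to reproduce, and the defect is one of wording. The check applies each rule to one test case: training is stopped for a week for intolerable joint pain, with no admission, no threat to life and no lasting disability.

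**Step 1: is it an AE?** Yes. The AE definition covers any unfavourable health occurrence after randomization.

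**Step 2: is it serious?**
- Opening sentence: yes. A temporary stop because the event is intolerable is enough.
- Criteria list: no. The first five criteria fail on the facts. The sixth, the important medical event, is tied to preventing one of the other serious outcomes, so an ordinary rest for pain would not meet it. A severe case might, by judgement.

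**Step 3: is it collected?** The answer depends on the judged relationship and on whether the words about association in the collection rule qualify only the nonserious AEs or the SAEs as well.

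| Judged relationship | Opening sentence | Criteria list |
|---|---|---|
| Possibly or Definitely Related | SAE, collected | Nonserious AE, collected |
| Not Related; association qualifies nonserious AEs only | SAE, collected | Nonserious AE, not collected |
| Not Related; association qualifies both | SAE, not collected | Nonserious AE, not collected |

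The seriousness label differs in every row. Whether the event is collected differs only in the second.

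**Step 4: what could the label change?** The documents give no rate for stops that meet no listed criterion, so the following is illustrative.
- Suppose two of the 12 resistance training participants have such a stop and nobody has any other SAE. The opening sentence gives 2/12 = 16.7% (exact 95% CI 2.1% to 48.4%). The list gives 0/12 = 0% (0% to 26.5%).
- Let p be the assumed share of the 12 with at least one such stop. The expected number is 12p, and the chance that at least one participant has one is 1 − (1 − p)^12.

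| Assumed p | Expected number of 12 | Chance of at least one |
|---|---|---|
| 0.05 | 0.6 | 0.460 |
| 0.10 | 1.2 | 0.718 |
| 0.20 | 2.4 | 0.931 |
| 0.30 | 3.6 | 0.986 |

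The last column is the chance that an event open to both readings occurs. It is not the chance that staff class it inconsistently, which also depends on the sentence they apply.

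**Step 5: which arm?** Resistance training has 3 × 14 = 42 planned sessions. For the comparator, "The comparator group will meet every 2 weeks" gives 14/2 = 7 meetings, or 14 if the same paragraph's mention of weekly workshops governs. The contact ratio is 42/7 = 6 or 42/14 = 3. This shows where opportunities for a stop lie; it is not an estimate of event rates.

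**The case against.** The strongest reply is that a practised reader would take the opening sentence as a loose description and the list as the operative rule. Two pieces of text support this. The list is the part tied to NIH guidelines. And the section gives, as an example of an ordinary AE, an event needing a physician visit because it affects the ability to exercise. Both points stand and make the list the better reading. They do not settle the matter: the opening sentence is itself worded as a definition, and the example does not set seriousness, since every SAE on the list is also an AE.

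A reader might infer that pain stops would commonly go unrecorded. The documents do not support that. Exacerbation of arthritis is listed as a risk of resistance training under Possible Discomforts and Risks, and Not Related is reserved for events clearly unrelated. A flare during training would therefore usually be Possibly Related and collected under either definition. Where a stop is judged Not Related, the loss is of the AE record only: Borg CR10 session ratings and the monitoring of missed visits would still leave a trace.

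A reader might also take the SAE count to be the main safety figure sent to the DSMB and IRB. The Data Safety and Monitoring Board section says that the board meets annually and that its reports go to the IRB; it does not describe their content. Related nonserious AEs are reported too.

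Finally, the broad definition over-reports, which is the cautious direction. That is true, but it does not excuse leaving two definitions in force.

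**Conclusion.** The point holds as an inconsistency in a stated rule. One event, a temporary stop of training for pain that meets no listed criterion, is an SAE under one sentence and a nonserious AE under the next, and the plan does not say which governs, although the list is favoured.

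The main effect is on the seriousness label. Loss of the AE record is confined to stops judged Not Related: under the list reading alone if association qualifies only nonserious AEs, and under both readings if it qualifies SAEs too. The size cannot be derived from the documents; the 2/12 against 0/12 contrast and the 5% to 30% range rest on assumed rates. It would be tempting to read the 46% to 99% range as the probability of misclassification, but it is only the chance that an eligible event occurs at those rates.

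No sample size, error rate or efficacy analysis is touched. The change should still be made, because safety belongs to the primary objective and the correction alters what is recorded and reported at little cost.

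**What to change.** In the adverse event section:

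1. State that an AE is serious only if it meets at least one criterion on the list.
2. Turn the opening sentence into a separate category: *AE leading to a temporary or permanent stop of the intervention or study procedures*.
3. Collect that category in both arms whatever the judged relationship, as an explicit exception to the rule that limits nonserious AEs to associated ones. This also removes the dependence on how the association wording is parsed for these events.
4. Report to the DSMB, by arm, the participants with an SAE and the participants with an AE leading to a stop.

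The cost is a few sentences of amendment and one item on the AE form (stop yes or no, with dates). No visits or staff are added. There are two downsides: fewer events carry the SAE label than under the opening sentence, so the table of stops must reach the DSMB to keep them visible; and a few more records are collected.
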